### **Use of Placebo**

33. The benefits, risks, burdens and effectiveness of a new intervention must be tested against those of the best proven intervention(s), except in the following circumstances:
  - Where no proven intervention exists, the use of placebo, or no intervention, is acceptable; or
  - Where for compelling and scientifically sound methodological reasons the use of any intervention less effective than the best proven one, the use of placebo, or no intervention is necessary to determine the efficacy or safety of an intervention

and the patients who receive any intervention less effective than the best proven one, placebo, or no intervention will not be subject to additional risks of serious or irreversible harm as a result of not receiving the best proven intervention.

Extreme care must be taken to avoid abuse of this option.

### **Post-Trial Provisions**

34. In advance of a clinical trial, sponsors, researchers and host country governments should make provisions for post-trial access for all participants who still need an intervention identified as beneficial in the trial. This information must also be disclosed to participants during the informed consent process.

### **Research Registration and Publication and Dissemination of Results**

35. Every research study involving human subjects must be registered in a publicly accessible database before recruitment of the first subject.
36. Researchers, authors, sponsors, editors and publishers all have ethical obligations with regard to the publication and dissemination of the results of research. Researchers have a duty to make publicly available the results of their research on human subjects and are accountable for the completeness and accuracy of their reports. All parties should adhere to accepted guidelines for ethical reporting. Negative and inconclusive as well as positive results must be published or otherwise made publicly available. Sources of funding, institutional affiliations and conflicts of interest must be declared in the publication. Reports of research not in accordance with the principles of this Declaration should not be accepted for publication.

### **Unproven Interventions in Clinical Practice**

37. In the treatment of an individual patient, where proven interventions do not exist or other known interventions have been ineffective, the physician, after seeking expert advice, with informed consent from the patient or a legally authorised representative, may use an unproven intervention if in the physician's judgement it offers hope of saving life, re-establishing health or alleviating suffering. This intervention should subsequently be made the object of research, designed to evaluate its safety and efficacy. In all cases, new information must be recorded and, where appropriate, made publicly available.

**Clinical Study Code: 20ANE-3489C**

**Sponsor Study Code: ETR01-E**

Without regard to the suspicious causality with the study drug, all adverse events which have the following characteristics will be reported via filling this form.

All serious adverse events which;

- ◆ Results in death, is life threatening,
- ◆ Requires inpatient hospitalization or prolongs inpatient hospitalization,
- ◆ Results in persistent or significant disabling/ incapacity, results a congenital anomaly/birth defect,
- ◆ Results in serious medical event (which threatens volunteer's life and may requires medical/surgical operation to prevent the results mentioned above).

INITIAL REPORT 	FOLLOW-UP REPORT 
INITIALS OF THE NAME AND SURNAME OF THE VOLUNTEER:	
VOLUNTEER NO:	                                                      
GENDER:	 FEMALE  MALE
DATE OF BIRTH:	           /            /            (dd)      (mmm)      (yyyy)
HEIGHT:	
WEIGHT:	
MEDICAL HISTORY OF THE VOLUNTEER:	

**ETORICOXIB 120 mg film-coated tablets**  
**Clinical Study Protocol Final Version 01, 23.DEC.20**

Screening No: |\_\_\_\_\_|\_\_\_\_\_|\_\_\_\_\_|\_\_\_\_\_|

and/or

Volunteer No: | \_\_\_\_\_ |

## THE STUDY DRUG:

**(in blinded studies, all the drugs which are likely to be taken by the volunteer should be specified)**

**THE ONSET DATE OF THE VOLUNTEER TO THE ACTIVE STUDY DRUG:**

\_\_\_\_\_ / \_\_\_\_\_ / \_\_\_\_\_

## **CONCOMITANT MEDICATIONS (PHARMACEUTICALS OR NONPHARMACEUTICALS)**

**DESCRIPTION OF THE SERIOUS ADVERSE EVENT:**

## ONSET DATE OF THE SERIOUS ADVERSE EVENT:

\_\_\_\_\_ / \_\_\_\_\_ / \_\_\_\_\_  
**(dd)      (mmm)      (yyyy)**

Screening No:

and/or

Volunteer No: \_\_\_\_\_

## THE PROCESS FOLLOWED FOR THE SERIOUS ADVERSE EVENT:

DOSAGE OF THE STUDY DRUG (tick only one)	 Not changed  Increased  Decreased  Temporarily stopped  Treatment finalized
VOLUNTEER IS WITHDRAWN	
VOLUNTEER IS TREATED specify	
OTHER specify	
NO TREATMENT	

## **CESSATION OF THE SERIOUS ADVERSE EVENT**

Screening No: |\_\_\_\_\_|\_\_\_\_\_|\_\_\_\_\_|\_\_\_\_\_|

and/or

Volunteer No: |\_\_\_\_\_|\_\_\_\_\_|\_\_\_\_\_|\_\_\_\_\_|

IS AUTOPSY DONE:	 Yes	 No	 Not determined
IF YES, SPECIFY THE DETAILED FINDINGS:			
COMMENTS AND ADDITIONALS*:			

\* Other additional information may be added to this section. Furthermore if this a follow-up report; the information which is different from the first report may be reported in this section.

INVESTIGATOR			
NAME AND SURNAME:			
PHONE:			
E-MAIL:			
ADDRESS:			

## **Appendix**

### **21.4. Acceptable Time Windows for Post-dose Clinical Procedures**

## Acceptable Time Windows for Post-dose Clinical Procedures

Scheduled post-dose clinical procedures should be performed within the below time windows. Procedures performed outside of these windows will be considered protocol deviations and will be reported in the CSR.

Procedure	Time window
200 mL of water (Day 1)	+ 5 min
Lunch (Day 1)	+ 10 min
Dinner (Day 1)	- 10 min / + 10 min
AE checks	- 30 min / + 30 min
Vital signs	- 10 min / + 30 min

4 STUDY OBJECTIVES

To evaluate and compare the bioavailability and therefore to assess the BE between a Test formulation of Exib 120 mg film-coated tablets (FCT) manufactured by PrJSC “Pharmaceutical firm “Darnitsa” (Ukraine) and a Reference formulation of Arcoxia®120 mg FCT manufactured by Merck Sharp&Dohme B.V. (The Netherlands) when administered orally at the same dose level to 28 healthy volunteers under fasting conditions, in a 2-way crossover design.

5 SCOPE OF ANALYSIS PLAN

This Statistical Analysis Plan (SAP) covers the bioequivalence assessment for study 20ANE-3489C, which will be performed by Medical Statistics Core Facility (MedStats) of IDIBAPS-Hospital Clinic. The SAP will follow the general regulatory recommendations given in the Guideline on the Investigation of Bioequivalence [1], as well as others specific guidance on methodological and statistical issues in bioequivalence studies [2].

6 SOFTWARE METHODS

The determination of pharmacokinetic (pk) parameters will be carried out using Phoenix® WinNonLin® v8.2 or an upgraded version [3] and the pharmacokinetic analysis will be performed with the SAS® System [4](Release 9.4 or an upgraded version).

All tables, figures and listings will be presented in WinWord (Version Microsoft Office 2007) documents.

7 STUDY DESIGN

This is an open-label, two-period, two-sequence, two-way crossover, randomised, single dose bioequivalence study in healthy male volunteers under fasting conditions. Treatment periods will be separated with a washout period of at least 14 days.

Each study subject will be randomly assigned (in accordance with the Randomization List) to receive one FCT of either Test or Reference medication on Day 1 of each study period.

The following measures will be implemented to reduce bias:

- Subjects will be sequentially assigned to receive either Test or Reference product in a random fashion.
- Eligibility of subjects will be based on the fulfillment of all study inclusion and exclusion criteria.
- The Clinical Unit (CU) staff will monitor and record subject's compliance and any non-compliance with the protocol requirements.

The Bioanalytical Laboratory staff will not have access to the study Randomization List.

8 JUSTIFICATION OF SAMPLE SIZE

Based on published data [5] [6] [7] [8], the highest intra-subject Coefficient of Variation (CV) following an oral single dose of etoricoxib 120 mg appears to be approximately 20% for C_{max} . Taking into account this value and assuming the a priori maximum difference of 5% between formulations, according to the approach of Zhang P [9] it is estimated that a sample size of 26 subjects in a two-period, two-sequence design should be sufficient to meet the bioequivalence (BE) range with a statistical a priori power of at least 90% with an alpha level protection of 0.05. Therefore, the inclusion of 28 subjects should be sufficient to also cover any potential drop-outs/withdrawals and variations around the estimated intra-subject CV.

To ensure that 28 volunteers are administered with the study medication, at least 2 standby subjects will remain at the CU until the last subject is dosed in the first study period.

9 RANDOMIZATION PROCEDURE

A number between 001 and 028 allocated to each subject after inclusion represents the randomization number (subject study number) of the subject. The numbers will be allocated to each volunteer according to the order of admission to the CU in Period 1.

The randomization list was generated using the software: proc Plan of SAS® System (Release 9.4 or an upgraded version), which assigns random numbers and treatments/periods to subjects.

The following table shows the generated volunteers randomization.

Subject	StudyId	Sequence	P1	P2
001	20ANE-3489C	TR	T	R
002	20ANE-3489C	RT	R	T
003	20ANE-3489C	TR	T	R
004	20ANE-3489C	RT	R	T
005	20ANE-3489C	TR	T	R
006	20ANE-3489C	RT	R	T
007	20ANE-3489C	TR	T	R
008	20ANE-3489C	RT	R	T
009	20ANE-3489C	RT	R	T
010	20ANE-3489C	TR	T	R
011	20ANE-3489C	RT	R	T
012	20ANE-3489C	TR	T	R
013	20ANE-3489C	TR	T	R
014	20ANE-3489C	RT	R	T
015	20ANE-3489C	TR	T	R
016	20ANE-3489C	RT	R	T
017	20ANE-3489C	TR	T	R
018	20ANE-3489C	RT	R	T
019	20ANE-3489C	TR	T	R
020	20ANE-3489C	RT	R	T
021	20ANE-3489C	TR	T	R
022	20ANE-3489C	RT	R	T
023	20ANE-3489C	RT	R	T
024	20ANE-3489C	TR	T	R
025	20ANE-3489C	RT	R	T
026	20ANE-3489C	TR	T	R
027	20ANE-3489C	RT	R	T
028	20ANE-3489C	TR	T	R

Treatment T:

Exib 120 mg film-coated tablets.

Manufactured by: PrJSC "Pharmaceutical firm "Darnitsa". Ukraine

Treatment R:

Arcoxia® 120 mg film-coated tablets.

Manufactured by: Merck Sharp&Dohme B.V., The Netherlands

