21.1. Declaration of Helsinki	
21.2. Informed Consent Form and Subject Information Sheet	
21.3. Form For Serious Adverse Events Reports	
21.4. Acceptable Time Windows for Post-dose Clinical Procedures	

## 1. STUDY SYNOPSIS

Title of Study	Randomized, open-label, single-dose, two-sequence, two-period, crossover, comparative, oral bioequivalence study of Exib 120 mg etoricoxib film-coated tablets (PrJSC "Pharmaceutical firm "Darnitsa") and Arcoxia 120 mg etoricoxib film-coated tablets (Merck Sharp&Dohme B.V.) in healthy, adult volunteers under fasting conditions.
Clinical Study Code	20ANE-3489C
Sponsor Study Code	ETR01-E
Phase	Phase I (Bioequivalence)
Sponsor	PrJSC "Pharmaceutical firm "Darnitsa", Ukraine
Clinical Unit	Erciyes University Hakan Cetinsaya GCP and Research Center, Turkey
Global CRO	Anapharm Europe, S.L.U., Spain
Bioanalytical Laboratory	Anapharm Europe, S.L.U., Spain
Statistics Facility	Medical Statistics Core Facility, IDIBAPS – Hospital Clinic Barcelona, Spain

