## 7.2. Measures to Minimise Bias

The following measures to reduce bias will be implemented:

- Subjects will be sequentially assigned to receive either Test or Reference product in a random fashion.
- Eligibility of subjects will be based on the fulfilment of all study inclusion and exclusion criteria.
- The CU staff will monitor and record subject's compliance and any non-compliance with the protocol requirements.

The Bioanalytical Laboratory staff will not have access to the study randomisation list.

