#### **10.3. Study Randomisation List**

The study randomisation list will be generated by the Project Statistician using the validated software proc Plan of SAS® System (release 9.4 or an upgraded version) (3) and will be based on the design, number of subjects and sequence of treatments to be administered in the study. The allocation of each treatment sequence to each subject will be done in such a way that the study is balanced. The Randomisation List will be signed and dated by the Project Statistician prior to implementation.

The randomisation list will not be made available to the Bioanalytical Laboratory staff during the study.

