#### **14.4. Bioanalytical Assay**

All pk blood samples obtained from all dosed subjects will be assayed.

Etoricoxib plasma concentrations will be determined using a validated bioanalytical LC/MS/MS method in compliance with the applicable EMA regulations (5) and GLP.

The Bioanalytical Protocol must be signed off prior to the start of pk sample analysis. A Bioanalytical Report will be issued to the Sponsor by the bioanalytical laboratory after completion of bioanalysis.

The bioanalytical laboratory staff will not have access to the study randomisation list.

No pk sample analysis will be repeated due to pk reasons.

In order to establish the reproducibility of the assay, incurred samples assessment will be performed according to applicable EMA regulations (5).

Bioanalytical sample analysis will only start after the last study pk sample has been collected.

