11.4 Pharmacokinetic Parameters Determination

The pharmacokinetic parameters will be estimated according to a non-compartmental approach with a log-linear terminal phase assumption using the drug concentration profiles and the actual sampling times with Phoenix WinNonLin v8.2 or an upgraded version [3]. Values below the lower limit of quantification in the absorption phase and in the terminal phase will be set to zero. AUC_{0-72h} (or AUC_{0-t} , if applicable) will be calculated using the mixed model linear log trapezoidal rule.

Missing concentration will be treated as missing (no value) in pharmacokinetic parameters calculation.

The Global CRO will provide the Medical Statistics Core Facility (MedStats) of IDIBAPS-Hospital Clínic with the etoricoxib plasma concentrations and the actual sampling times.

Actual sampling times will be listed for each subject by period.

For AUC_{0-72h} (or AUC_{0-t} , if applicable) calculation, the linear trapezoidal rule will be used up to C_{max} , according to this formula:

$$AUC \left|_{t_1}^{t_2} = \delta_t * \frac{C_1 + C_2}{2}$$

and the log trapezoidal rule from then to the last time measurement:

$$AUC \left|_{t_1}^{t_2} = \delta_t * \frac{C_1 - C_2}{\ln\left(\frac{C_1}{C_2}\right)}$$

where $\delta_t = (t_2 - t_1)$.

In case $AUC_{0-\infty}$ is calculated, it will be done by extrapolating to infinity AUC_{0-t} , by means of the following formula:

$$AUC_{0-\infty} = AUC_{0-t} + C_n \lambda_z$$

where the C_n is the last concentration measured, and λ_z is the terminal rate constant obtained by the slope ($\lambda_z = -1 * \text{estimated slope}$) of the log-linear regression analysis on data points assessed to be on the terminal log-linear phase.

The selection of the data points of the terminal log-linear phase will be obtained automatically by WinNonLin® (using at least three available above LLOQ concentration points occurring after C_{max}).

The extrapolation to infinity will be performed by regression with the last log-transformed data to estimate the terminal area by means of the line which maximized R^2 . The R^2 is calculated by WinNonLin® according to this formula:

$$R^2 = 1 - \frac{(1 - R^2)(n - 1)}{(n - 2)}$$

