18 APPENDIX 1 – RANDOM LIST

RANDOM LIST CLINICAL STUDY CODE 20ANE-3489C

Subject	StudyId	Sequence	P1	P2
001	20ANE-3489C	TR	T	R
002	20ANE-3489C	RT	R	T
003	20ANE-3489C	TR	T	R
004	20ANE-3489C	RT	R	T
005	20ANE-3489C	TR	T	R
006	20ANE-3489C	RT	R	T
007	20ANE-3489C	TR	T	R
008	20ANE-3489C	RT	R	T
009	20ANE-3489C	RT	R	T
010	20ANE-3489C	TR	T	R
011	20ANE-3489C	RT	R	T
012	20ANE-3489C	TR	T	R
013	20ANE-3489C	TR	T	R
014	20ANE-3489C	RT	R	T
015	20ANE-3489C	TR	T	R
016	20ANE-3489C	RT	R	T
017	20ANE-3489C	TR	T	R
018	20ANE-3489C	RT	R	T
019	20ANE-3489C	TR	T	R
020	20ANE-3489C	RT	R	T
021	20ANE-3489C	TR	T	R
022	20ANE-3489C	RT	R	T
023	20ANE-3489C	RT	R	T
024	20ANE-3489C	TR	T	R
025	20ANE-3489C	RT	R	T
026	20ANE-3489C	TR	T	R
027	20ANE-3489C	RT	R	T
028	20ANE-3489C	TR	T	R

Treatment T:

Exib 120 mg film-coated tablets.
Manufactured by: PrJSC "Pharmaceutical firm "Darnitsa". Ukraine

Treatment R:

Arcoxia® 120 mg film-coated tablets.
Manufactured by: Merck Sharp&Dohme B.V., The Netherlands

The randomisation scheme has been created using a list of randomised numbers obtained by Proc Plan procedure of SAS software version 9.4.

Project Statistician:

Date:

Signature

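### Does printing the full randomisation list in the SAP break the masking of the bioanalytical laboratory?

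*SAP*

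**What the plan says.** SAP Section 7, after its measures against bias, says "The Bioanalytical Laboratory staff will not have access to the study Randomization List". Protocol Sections 7.2 and 14.4 say the same, and Protocol Section 10.3 adds a time frame: "The randomisation list will not be made available to the Bioanalytical Laboratory staff during the study".

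SAP Section 9 then introduces a table with "The following table shows the generated volunteers randomization" and lists the sequence and the product given in each period for subjects 001 to 028. Appendix 1, headed "RANDOM LIST CLINICAL STUDY CODE 20ANE-3489C", prints the list again.

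The protocol synopsis enters "Anapharm Europe, S.L.U., Spain" for both the Global CRO and the Bioanalytical Laboratory. SAP Section 5 assigns the bioequivalence assessment to a different organisation, the statistics facility at IDIBAPS–Hospital Clinic. SAP Section 11.4 has the Global CRO send that facility the concentrations and actual sampling times. Under Protocol Section 14.3, each aliquot label shows the subject (or standby) number, the period and the sample number.

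**The concern.** Keeping the list from the laboratory is the only masking described in this open-label trial. The SAP promises that masking and then carries the complete code, twice. Because one company fills both roles, a copy of the SAP sent to its CRO side would already be inside the laboratory's own organisation. An analyst holding it could read the treatment for a sample from the label.

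The laboratory's judgements matter. SAP Section 11.1 sets a concentration to missing when it cannot be determined for bioanalytical reasons, and SAP Section 11.2.1 takes Cmax directly from the observed values. One such decision near the peak can therefore move a primary parameter. If those decisions were made with knowledge of treatment, the Cmax and AUC comparisons could be biased, and an inspector could ask how the promise was kept.

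**Working it through.** There is no statistical figure to recompute here. The check is a count, followed by a comparison of what the documents restrict with what they print.

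1. **The list.** Section 9 and Appendix 1 each show 28 subjects, 14 in sequence TR and 14 in RT. The two copies agree line by line, so this is one list printed twice.

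2. **What it could decode.** Inputs: 28 subjects (SAP Section 9), 2 periods, and 20 samples per period (SAP Section 10). The ceiling is 28 × 2 × 20 = 1,120 samples. Under Protocol Section 11.2.12 a standby subject who replaces someone keeps a number such as S001, which is not on the list. Each replacement who completes both periods therefore removes 2 × 20 = 40 samples from what the list decodes by itself. With two replacements the figure is 1,120 − 80 = 1,040. Missed samples and drop-outs lower it further.

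3. **What is restricted.** All four statements (SAP Section 7; Protocol Sections 7.2, 10.3 and 14.4) bar laboratory staff from the list. None is limited to one physical copy, so a SAP that contains the list falls under the same rule.

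4. **Who uses the SAP.** It covers work done by the statistics facility, which needs the code to fit the model in SAP Section 11.5.1. The described data flow runs from the Global CRO to that facility. No available section sends the SAP to laboratory staff.

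5. **Where else the code exists.** Under Protocol Section 10.4 the unit-dose labels show subject number, period and treatment letter. Under Section 11.3.2 the tear-off part goes on the CRF. In an open-label study the code is in several study records by design, so the protection comes from the access rule.

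6. **Other limits on laboratory discretion.** Protocol Section 14.4 requires a validated method, a signed bioanalytical protocol before analysis, incurred-sample assessment, no repeat assays for pharmacokinetic reasons, and no assay before the last sample is collected. Section 16.4 provides for quality control and audit. Under SAP Section 11.1 the Sponsor decides exclusions for unreliable profiles before the assay starts.

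7. **Effect on planned quantities.** The sample size (SAP Section 8) uses a CV, an assumed difference, power and alpha. The model, confidence interval and limits are in SAP Section 11.5. None of these depends on where the list is filed.

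**The case for a change.** The strongest case for a change is that the SAP does not need the list. The model and population are fully specified without it, and its users are the project statistician and the Clinical Unit staff who package doses. The Global CRO must agree protocol amendments and signs the study report, so it could plausibly receive the SAP. No internal separation between its CRO and laboratory functions is described in the available text. The measures in Protocol Section 14.4 constrain the laboratory but do not mask its decisions. Taking the table out, or adding a sentence on circulation, would cost almost nothing.

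Much of this stands: a separate restricted file would be cleaner, and it would make the masking easier to demonstrate at inspection. What does not stand is the step from a list printed in the SAP to masking that has failed. That step needs laboratory staff to hold the SAP before their data are final, and nothing available says so. The SAP's front pages were removed from the reviewed copy, so a restriction on circulation cannot be said to be absent. The latest web-access date in the SAP references is 23 February 2021, but no assay date is given, so the order of events is also unknown. Having both roles in one company is a matter of internal separation, which moving a table does not alter.

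**Conclusion.** The plan needs no change on this point. Followed as written, it keeps the list, and therefore any document that contains it, away from laboratory staff. The concentrations are then produced under the intended masking, and the results are sound. Printing the code in the SAP leaves a document-control matter that the study team can settle when it circulates the document.

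The exposure if the rule were broken is at most 1,120 samples, fewer with standby replacements or missing samples. The size of any resulting bias cannot be derived from the documents. The conclusion assumes that SAP circulation follows the stated access rule. Evidence that an analyst held the list before the bioanalytical data were final would show a deviation in conduct from a rule the plan already contains.

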10 TIME POINTS FOR PHARMACOKINETIC SAMPLES

The following table shows the pharmacokinetic samples schedule for each study period.

Sample No.	Sampling Time (h)
01	0.000 (Pre-dose)
02	0.083
03	0.167
04	0.250
05	0.333
06	0.500
07	0.750
08	1.000
09	1.250
10	1.500
11	2.000
12	3.000
13	4.000
14	6.000
15	8.000
16	12.000
17	24.000
18	36.000
19	48.000
20	72.000

